Study product / intervention:	
Azithromycin Pfizer® powder for oral suspension will be used in the active comparator arm. Patients in MYTHIC will be randomized 1:1 either to azithromycin (active group: 1 daily dose for 5 days, 10mg/kg/day on day 1 and 5mg/kg/day on days 2-5) or matching placebo (control group: 5 days of placebo). The doses used in MYTHIC differ from the Swissmedic-approved prescribing information (3-day regimen), but are in accordance with the FDA-approved prescribing information for CAP (5-day regimen) to achieve globally accepted study results.

Control intervention:	
Children in the control arm will be receiving oral placebo matched to the product described above and supplied by the ZüriPharm AG (former Kantonsapotheke Zürich), Zurich, Switzerland.

Number of participants with rationale:	
Under the assumptions outlined below, 376 patients will be recruited for the intervention phase of the trial. Based on previous studies, we assume that 66.7% of the patients agree to screening (and study participation) and that 15% of screened patients will have a positive Mp IgM LFA result, resulting in 10% of screened patients available for recruiting into the intervention phase of the study ($0.67 \times 0.15 = 0.10$). Thus, we expect that the number of patients to screen is 3,760.

Study duration:	
Total duration: 60 months Recruitment period: 48 months

Study schedule:	
07/2024 First-Participant-In (planned) 06/2028 Last-Participant-Out (planned)

Investigators:	
Coordinating principal investigator: PD [name]. med. [name]
 
Local principal investigators:
 
 PD Dr. med. [name] (University Children's Hospital Zurich) [name]. med. [name] (Triemli Hospital Zurich) Dr. med. [name] (Cantonal Hospital Winterthur) PD [name]. med. [name] (University of Basel Children's Hospital) Dr. med. [name] (Children's Hospital of Eastern Switzerland St. Gallen) Dr. med. [name] (Cantonal Hospital Graubünden)

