Statistical considerations:	
Multiplicity with two co-primary endpoints was handled using the “at least one” success criterion: We estimated the sample size for both co-primary endpoints for a one-sided significance level of 1.25% and a power of 80%, and use the larger of the two sample sizes for the trial. This assures a minimum power of 80% to reject at least one null hypothesis.
 
The co-primary endpoint time to normalization of all VS is considered as a time-to-event endpoint. The sample size was estimated assuming an overall event rate of 99% and a hazard ratio of 1 for placebo vs. macrolide (a hazard ratio <1 would indicate longer duration with placebo than with macrolide). The sample size was estimated to show the non-inferiority of placebo vs. macrolide in Mp PCR-positive patients using a non-inferiority margin of 0.7 for the hazard ratio. Considering a drop-out rate of 14.5%, 354 patients should be recruited for the intervention phase of this study (302 evaluable patients).
 
For the co-primary endpoint CAP-related change in patient care status (binary) we expect an absolute risk of 5% in both trial arms and thus an absolute risk difference (ARD, $risk_{macrolide} - risk_{placebo}$) of 0 between the two arms. An ARD <0 would indicate a higher risk with placebo than macrolide. The sample size was estimated to show the non-inferiority of placebo vs. macrolide in Mp PCR-positive patients, using a non-inferiority margin of -7.5% for the ARD. Considering a drop-out rate of 14.5%, 376 patients should be recruited for the intervention phase of this study (322 evaluable patients).

GCP statement:	
This study will be conducted in compliance with the protocol, the current version of the Declaration of Helsinki, ICH-GCP, as well as all national legal and regulatory requirements.

ABBREVIATIONS

AE	Adverse event
AESI	Adverse event of special interest
AMR	Antimicrobial resistance
AR	Adverse reaction
ARD	Absolute risk difference
ASC	Antibody-secreting cell
ASR	Annual safety report
BASEC	Business Administration System for Ethical Committees (https://submissions.swissethics.ch/en/)
BTS	British Thoracic Society
CA	Competent authority (e.g., Swissmedic)
CAP	Community-acquired pneumonia
CEC	Competent ethics committee
CI	Confidence interval
ClinO	Ordinance on Clinical Trials in Human Research (in German: KlinV, in French: OClin, in Italian: OSRUm)
CTCAE	Common terminology criteria for adverse events

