Cohort, n	Characteristics	Reference test PCR	Screening test IgM LFA		Performance
			Positive (grade 2 or 3)	Negative (grade 0 or 1)	
myCAP study ($n=94$, published in [74]) and KIDS-STEP study ($n=31$, unpublished results) $n=125$ (total)	
 • CAP clinically diagnosed • Age 3-17 years • Inpatients or outpatients • Previous healthy children 	Positive	37 (29.6%)	6 (4.8%)	Sensitivity: 86.0% (95% CI 72.7%-93.4%) Specificity: 95.1% (95% CI 88.1%-98.1%) LR+: 17.64 (95% CI 6.73-46.22) LR-: 0.15 (95% CI 0.07-0.31) DOR: 120.25 (95% CI 31.99-452.07)
		Negative	4 (3.2%)	78 (62.4%)	

Abbreviations: CI, confidence interval; DOR, diagnostic odds ratio; LR+, positive likelihood ratio; LR-, negative likelihood ratio.

All screened and enrolled participants will provide a NPS sample (see Study flow), either performed as part of the clinical routine diagnostic work-up or exclusively for the use in this study. All collected NPS samples will be tested with an **Mp PCR** as reference test to verify the **Mp IgM LFA** test result. **Mp IgM LFA** false-positive participants will be excluded from the per protocol analyses (Table 5). All NPS samples will be frozen and stored locally (-20°C to -80°C depending on the infrastructure of the center). The stored NPS samples will be transferred to and analyzed by **Mp PCR** at University Children's Hospital Zurich. The results of the **Mp PCR** will not be available before the close-out visit on day 28. In case a **Mp PCR** (single- or multiplex) is performed for clinical reasons, and indicates a false-positive **Mp IgM LFA**, participants will be followed up until the close-out visit on day 28 (Table 5).

Enrollment

The **Mp IgM LFA** results will be available within 10min. In case of a positive **Mp IgM LFA** result, the local investigators will carefully check for eligibility, and obtain written informed consent for participation in the intervention phase of the trial (enrollment).

For enrolled children, a venous blood sample for the **Mp IgM ASC ELISpot assay** is required. This venous blood sample is often already routinely available (IV line and/or venous blood sampling is performed for clinical reasons in many CAP patients). However, to avoid exclusion of patients due to refusal to drawing a venous blood sample, this venous blood sample is not required for inclusion into the study. The results of the **Mp IgM ASC ELISpot assay** for the study will not be available before study closure.

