11.2 Determination of sample size

Sample size calculations were done with regard to the per protocol set (PPS), which includes patients who are positive for *Mp* by PCR (section 6.1, Table 5). To handle multiplicity with two co-primary endpoints, we apply the “at least one” success criterion [83]: We estimated the sample size for both co-primary endpoints at a one-sided significance level (α) of 1.25% (which corresponds to two-sided 97.5% confidence intervals [CI]) and a power of 80% ($\beta=20\%$), and use the larger of the two sample sizes for the trial. This assures a minimum power of 80% to reject at least one null hypothesis.

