The primary endpoint **time to normalization of all VS** is considered as a time-to-event endpoint, i.e., the number of days until normalization. Although we expect all patients to normalize VS during the 28-day FUP period, we used an overall event rate of 99% for the sample size calculation, in order to allow censoring. This endpoint will be compared between trial arms by a Cox proportional hazards model to estimate a hazard ratio for placebo vs. azithromycin (a hazard ratio <1 would indicate longer duration to normalization with placebo than with azithromycin). We expect no difference between treatments and thus a hazard ratio of 1. The sample size was estimated to show the non-inferiority of placebo vs. azithromycin treatment in *Mp* PCR-positive patients using the method given in Chow et al. [84] (page 177), with a non-inferiority margin (δ_{HR}) of 0.7 for the HR. Assuming exponential survival times (with an overall event rate of 99% within 28 days), this non-inferiority margin of 0.7 would be equivalent to the inverse ratio of median survival times, which would be 4.8 days for placebo and 3.3 days for azithromycin (with a HR of 1 the median survival time would be 4.2 days). The maximum prolongation of the duration to VS normalization by 1.5 days may be acceptable from a clinical perspective, especially when weighed against side effects, effect of antibiotics on microbiome, increased antibiotic resistance, and costs. These aspects are also discussed for patients with group A β -hemolytic streptococcal pharyngitis, in which modest effects of antibiotics have been observed (symptomatic improvement by only 1-2 days) [85]. Under the assumptions stated above, 302 *Mp* PCR-positive patients are needed for this study (Figure 2). Considering a drop-out rate of 14.5%, 354 patients should be enrolled. This drop-out rate is calculated from an expected drop-out of 10% due to negative *Mp* PCR (false-positive screening by *Mp* IgM LFA, section 6.1, Table 5) and an additional overall drop-out rate of 5% (due to loss to FUP or insufficient compliance), i.e., $0.1 + 0.05 \cdot (1 - 0.1) = 0.145$ (14.5%).

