The co-primary endpoint **CAP-related change in patient care status** (binary) will be compared in terms of the absolute risk difference (ARD) between the two arms ($ARD = \text{risk}_{\text{azithromycin}} - \text{risk}_{\text{placebo}}$, $ARD < 0$ would indicate a lower risk with macrolide than placebo). We expect an absolute risk for this unfavorable event of 5% in both trial arms and thus an ARD of 0. The sample size was estimated to show the non-inferiority of placebo vs. macrolide treatment in *Mp* PCR-positive patients, using the method given in Chow et al. [84] (page 90), with a non-inferiority margin (δ_{ARD}) of -7.5% for the ARD (Figure 3). This non-inferiority

would allow a maximum event rate of 12.5% in the placebo arm, which is less than 13.5%, the median acceptable failure rate in treatment of CAP identified in a survey of infectious disease physicians [86, 87]. Under the assumptions stated above, 322 *Mp* PCR-positive patients are needed for this study. Considering a drop-out rate of 14.5% (as above), 376 patients should be enrolled.

As we consider the larger of these two sample sizes (above), 376 patients should be recruited for the trial. We assume that 66.7% of patients agree to screening and study participation (according to [22] and unpublished observations in KIDS-STEP [75] at participating center Zurich) and that 15% of screened patients are *Mp*-positive (section 3.1), which results in 10% of screened patients available for recruiting ($0.67 \times 0.15 = 0.10$).

Thus, we expect that the number of patients to screen is 3,760.

Figure 2. Sensitivity of the sample size for the co-primary endpoint duration to normalization of VS with regard to the non-inferiority margin, δ_{HR} , expecting no difference between treatments (HR=1).

[figure not shown]
[figure not shown]

Figure 3. Sensitivity of the sample size for the co-primary endpoint CAP-related change in patient care status with regard to the non-inferiority margin, δ_{ARD} , expecting no difference between placebo and azithromycin (ARD=0), assuming a probability for a change in patient care status of 0.05.

Based on these considerations, the numbers of enrolled subjects predicted for each trial site is shown in Table 10:

Table 10. The MYTHIC Study timeline with predicted patient enrollment per trial site:

Years	1		2		3		4		5		Total
Months	1-6	7-12	13-18	19-24	25-30	31-36	37-42	43-48	49-54	55-60	
Study phases:											
Preparatory phase	X										

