11.4.4 Interim analyses

An interim analysis for safety will be conducted after $1/3$ and $2/3$ of the patients have completed the 28-day FUP (Table 10). The IDMC (section 1.6) will oversee and discuss the results. Access to interim data and interim analysis results will be limited to the IDMC and the statistician. We will do a blinded sample size review, using an internal pilot study design. The sample size review will be done for the binary co-primary endpoint, since the sample size estimation for this endpoint depends on the overall risk of a change in patient care status as a nuisance parameter [89]. The overall event rate for the time-to-event co-primary endpoint (proportion of patients with VS normalization within 28 days) is less uncertain and larger (less important nuisance parameter). We will estimate the overall risk of a change in patient care status ad interim, after 250 patients have the primary outcome measurement ($2/3$ of the planned sample size, \hat{N}_{init}), as the proportion of patients who had the event, ignoring treatment groups. This estimate of the overall risk will then be used to recalculate the sample size, \hat{N}_{recalc} , as described above in section 11.2. The final sample size will be the larger of the original sample size and the recalculated sample size, $\hat{N} = \max(\hat{N}_{init}, \hat{N}_{recalc})$.

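### The 10% allowance for PCR-negative children belongs to a pilot with 34% Mp prevalence; at the plan's own 15% it is 24–28%, leaving about 255–270 evaluable children instead of 322.

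*Protocol*

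**What the plan says.** Section 11.2 sizes both co-primary comparisons on the per protocol set (PPS), which is restricted to PCR-positive children. It uses one-sided 1.25% and 80% power per endpoint, takes the larger sample, and concludes: "This assures a minimum power of 80% to reject at least one null hypothesis". The requirement is 302 evaluable children for time to normalization of vital signs and 322 for change in care status.

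Both are enlarged for a 14.5% loss. "This drop-out rate is calculated from an expected drop-out of 10% due to negative" Mp PCR, with a further 5% for loss to follow-up or poor compliance. The section points to Table 5, where 4 of 41 LFA-positive pilot children (9.8%) were PCR-negative. Enrolment becomes 354 and 376.

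For the number to screen, section 11.2 assumes "15% of screened patients are *Mp*-positive (section 3.1"). The synopsis gives the same percentage for a different quantity: "15% of screened patients will have a positive" LFA result.

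Table 4 gives the pilot counts: 37 of 43 PCR-positive children were LFA-positive, and 4 of 82 PCR-negative children were ("Specificity: 95.1% (95% CI 88.1%-98.1"%).

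The blinded sample size review in section 11.4.4, after 250 patients, estimates the pooled risk of a care-status change. "This estimate of the overall risk will then be used to recalculate the sample size" by the method of section 11.2.

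**The concern.** The proportion of test-positives that are false is not a fixed property of a test. It depends on how common the condition is among those tested. The 10% was observed where about one child in three was PCR-positive, and it is applied to a trial planned on roughly one in seven. With Table 4's test performance, a 15% yield and a 10% false-positive share do not go together.

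The PPS is the set on which non-inferiority is concluded, so a larger PCR-negative share takes children directly out of both primary tests. The blinded review would not catch this. It updates only the event risk and otherwise carries the 14.5% forward; if the pooled risk is 5% or less, the total stays at 376. The full analysis set would also be about one quarter PCR-negative, which dilutes any treatment difference in the supporting analysis.

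**Working it through.** **1. The plan's own figures reproduce.** With z(0.9875) = 2.2414 and z(0.80) = 0.8416, (2.2414 + 0.8416)² = 9.505.

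- Vital signs: events = 4 × 9.505 / (ln 0.7)² = 38.02 / 0.1272 = 298.9, so 299. Patients = 299 / 0.99 = 302.
- Care status: n per arm = 2 × 0.05 × 0.95 × 9.505 / 0.075² = 160.5, so 161, or 322 in total.
- Loss: 0.10 + 0.05 × 0.90 = 0.145. 302 / 0.855 = 353.2 (stated 354), 322 / 0.855 = 376.6 (stated 376), and 376 × 0.855 = 321.5 evaluable.
- Power at that size: about 80% for care status and 83% for vital signs.

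**2. False-positive share as a function of prevalence.** From Table 4, sensitivity = 37/43 = 0.8605 and 1 − specificity = 4/82 = 0.0488. For PCR prevalence p:

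f(p) = 0.0488(1 − p) / [0.0488(1 − p) + 0.8605p]

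- Pilot, p = 43/125 = 0.344: f = 0.0320 / 0.3280 = 9.8%, the source of the 10%.
- Reading A, 15% PCR-positive (section 11.2): f = 0.0415 / 0.1705 = 24.3%. The LFA-positive rate would be 17.1%, so the two 15% statements are not the same assumption.
- Reading B, 15% LFA-positive (synopsis): p = (0.15 − 0.0488) / (0.8605 − 0.0488) = 0.125, and f = 0.0488 × 0.875 / 0.15 = 28.5%.

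**3. Evaluable children and power at 376 enrolled.** PPS size n = 376 × (1 − f) × 0.95.

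- Vital signs: power = Φ(√(0.99n/4) × |ln 0.7| − 2.2414)
- Care status: power = Φ(0.075 / √(2 × 0.0475/(n/2)) − 2.2414)

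| | PCR-negative | Combined loss | PPS | Power, vital signs | Power, care status | Enrolment for 322 evaluable |
|---|---|---|---|---|---|---|
| As stated | 10% | 14.5% | 321.5 | 83% | 80% | 377 |
| Reading A | 24.3% | 28.1% | 270.4 | 75.1% | 72.2% | 448 |
| Reading B | 28.5% | 32.0% | 255.5 | 72.4% | 69.5% | 474 |

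The PPS is 16% (270.4/322) to 21% (255.5/322) below the stated size. It is also below the 302 needed for the less demanding endpoint.

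**4. At-least-one power.** Whatever the dependence between the endpoints, only the larger single-endpoint power can be guaranteed: 75% or 72%. If the endpoints were independent, the figure would be 93% or 92%.

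**5. Sensitivity of the result.** At 15% PCR prevalence:

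- Specificity at its upper 95% limit (98.1%): f = 11%, PPS about 317, power 82% (vital signs) and 79.5% (care status).
- Specificity at its lower limit (88.1%): f = 44%, PPS about 200, power 61% and 58%.
- Sensitivity at its limits (72.7% and 93.4%): f = 28% and 23%.

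With Table 4's test performance and other prevalences cited in section 3.1:

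- 8%: f = 39%, PPS about 216.
- 18–19%: f = 21–19%, PPS about 284–288, power 77–78% and 74–75%.
- 29%: f = 12%, PPS about 314, power 82% and 79%.

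**The case against.** - **The 15% may be a deliberately low yield.** It is used only to derive the number to screen, where caution means assuming few positives. Section 3.1 cites 29% for ages 3–17, and the pilot applied the trial's own inclusion criteria. At 28–29% the shortfall is small. This stands as a possible explanation, but the protocol does not give it, and section 11.2 presents both figures as expectations for the same trial.
- **Specificity rests on 4 false positives in 82.** At the upper confidence limit the plan nearly holds. True, but a 10% share at 15% prevalence needs a specificity of about 98.3%, just beyond that limit, and most of the uncertainty makes the shortfall worse. The 24–28% are point estimates and should be given with a range.
- **Trial success needs only one endpoint.** Actual at-least-one power may well exceed 80%, up to 92–93% under independence. This stands. What fails is the claim of an assured minimum, together with the 80% per endpoint.
- **The event risk may be below 5%.** Section 5.1 expects at most 5%. With 270 evaluable, care-status power would be 82% at 4% risk and 91% at 3%; with 255, 79% and 90%. This is fair, but 5% is the value the plan uses for sizing.
- **Missing outcomes are multiply imputed (section 11.5), so the 5% loss is partly recovered.** With no such loss, reading A gives at most 376 × 0.757 = 285 children and power of 77% and 75%. The gap narrows but stays open.

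**Conclusion.** The point holds. The calculations in section 11.2 are internally correct, but they combine a false-positive share from a population with 34.4% prevalence with a planning rate of 15%. On the plan's own inputs, 376 enrolled children give about 255–270 evaluable instead of 322. Power is 72–75% for vital signs and 69–72% for care status, and the guaranteed minimum for at least one success is 72–75%, not 80%. It does not follow that at-least-one power is in fact below 80%; that depends on the correlation between the endpoints.

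The figures assume that the pilot sensitivity and specificity carry over, that 15% is the true planning rate, and that the 5% additional loss and 5% event risk apply. Type I error, margins and the analysis itself are unaffected. It needs correcting because the stated evaluable number and power for both primary tests are wrong as written, and a shortfall cannot be made good once recruitment has closed.

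**What to change.** 1. In section 11.2 and the synopsis, state one planning prevalence and say whether it refers to PCR-positive or LFA-positive children; the two 15% statements need reconciling.
2. Replace the 10% and 14.5% by the values that prevalence implies: at 15%, a PCR-negative share of 24–28% and a combined loss of 28–32%. Show the range over the confidence interval for specificity.
3. Restate the expected PPS (about 255–270 from 376), the power per endpoint (about 70–75%), and the guaranteed at-least-one minimum.
4. In section 11.4.4, add the PCR-positive share as a second nuisance parameter, pooled over arms and estimated from the stored day-1 swabs of the first 250 children. These swabs precede treatment, so blinding is kept. Table 5 puts PCR results after study closure and section 6.1 puts them no earlier than the day 28 visit; both need aligning with an interim batch.

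The cost is less favourable published figures, an amendment, and one earlier PCR batch on swabs that will be tested anyway. No extra patients are committed now. If the sponsor wishes to restore 322 evaluable children, enrolment of about 448 (322/0.719) to 474 (322/0.680) would be needed, and the review at 250 patients is a natural point to decide.

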the hospital or transfer to the ICU (safety). A recent U.S. study showed that re-admission occurred in 5% of children with CAP receiving beta-lactam monotherapy and in 2% receiving beta-lactam plus macrolide combination therapy [13]. In another U.S. CAP study, re-admission was reported in 0.5% of those who received beta-lactam monotherapy and in 0.6% of those who received beta-lactam plus macrolide combination therapy [64]. Detailed information about the proportion of patients with *Mp* infection was not available for both studies. Based on these data we expect a small proportion ($\leq 5\%$) of patients with a CAP-related change in patient care status.

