11.4.2 Primary analysis

To assess the non-inferiority of placebo vs. azithromycin regarding the co-primary endpoint **time to**

normalization of VS, we will estimate the hazard ratio of placebo vs. azithromycin with a two-sided 97.5% CI using a Cox proportional hazards model on the PPS (defined in section 11.4.1). Non-inferiority of placebo will be declared if the lower limit of the CI will be larger than the non-inferiority margin (i.e., the whole CI lies entirely above the margin).

To assess the non-inferiority of placebo vs. macrolide regarding the co-primary endpoint **CAP-related change in patient care status**, we will estimate the absolute risk difference ($ARD = risk_{azithromycin} - risk_{placebo}$) with a two-sided 97.5% CI on the PPS. Non-inferiority of placebo will be declared if the lower limit of the CI will be larger than the non-inferiority margin (i.e., the whole CI lies entirely above the margin).

The two non-inferiority tests will be performed and interpreted independently (of each other) and the trial considered successful if non-inferiority can be shown for at least one of the primary outcomes. Should the resulting CIs exclude the reference value for no difference (1 for hazard ratio, 0 for ARD), the result can be interpreted as superiority of either treatment [88].

To complement the main analyses above, the following sensitivity and additional analyses are planned:

- We consider the **PPS as the main set for showing non-inferiority** (section 6.1, Table 5), and the sample size calculation was also done with regard to the PPS (section 11.2). In addition, we will also test non-inferiority in the strict PPS and the FAS. Since the three analysis sets (FAS, PPS, and strict PPS) differ considerably in size and composition (section 6.1, Table 5), we will consider the PPS as the relevant set for concluding non-inferiority, but we will discuss differences in the conclusions based on the different sets. For a robust interpretation of the non-inferiority test these analyses should lead to similar conclusions as the main analysis [87].
- For CAP-related change in patient care status, we will present the 2×2 table of events per treatment arm and an unadjusted odds ratio (OR) estimate for all three analysis sets.
- For time to VS normalization, we will plot Kaplan-Meier curves and estimate median time-to-event by trial arm.

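### At 322 evaluable patients the stated 80% power and one-sided 1.25% error for the care-status co-primary do not hold together under any standard interval checked

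*Protocol*

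**What the plan says.** Protocol section 11.2 sizes each co-primary endpoint separately, "at a one-sided significance level (α) of 1.25% (which corresponds to two-sided 97.5% confidence intervals [CI"]), with 80% power, and takes the larger number. For the care-status endpoint the planning assumption is: "We expect an absolute risk for this unfavorable event of 5% in both trial arms and thus an ARD of 0". The margin for the absolute risk difference (ARD, azithromycin minus placebo) is -7.5 percentage points, which corresponds to a placebo risk of 12.5% when the azithromycin risk is 5%. The result is 322 "PCR-positive patients are needed for this study. Considering a drop-out rate of 14.5% (as above), 376 patients should be enrolled".

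On the two endpoints jointly, section 11.2 says: "This assures a minimum power of 80% to reject at least one null hypothesis".

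Section 11.4.2 tests the ARD "with a two-sided 97.5% CI on the PPS. Non-inferiority of placebo will be declared if the lower limit of the CI" lies above the margin. It does not name the type of interval.

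Section 11.4.4 plans a blinded review of the pooled risk for this endpoint: "This estimate of the overall risk will then be used to recalculate the sample size", by the section 11.2 method, with the larger of the original and recalculated sizes retained.

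**The concern.** The formula behind 322 uses only the variance expected when both arms have 5% risk. The test is made at a difference of 7.5 points, where the variance is larger. With about 8 expected events per arm (161 x 0.05), that difference is not negligible. An interval that uses the observed variances, as the formula does, tends to be too short when the truth lies at the margin. An interval that allows for the null variance is wider and has less power than the formula promises.

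This endpoint carries the safety claim of a placebo-versus-antibiotic trial in children. The trial counts as successful if either test succeeds, so splitting the error into two shares of 1.25% is its only multiplicity protection. A reader of section 11.2 will take both the 1.25% and the 80% as properties of this test.

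**Working it through.** **Inputs** (sections 6.2.1, 11.2 and 11.4.2): one-sided error 0.0125 (z = 2.241); power 0.80 (z = 0.842); risk 0.05 in each arm; margin 0.075; 1:1 allocation; drop-out 14.5%.

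**Step 1: reproduce the printed size.** Unpooled normal approximation:

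n per arm = (2.241 + 0.842)² x (2 x 0.05 x 0.95) / 0.075² = 9.505 x 0.095 / 0.005625 = 160.5, so 161 per arm and 322 in total.

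322 / 0.855 = 376.6, printed as 376. The plan's figures are reproduced.

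**Step 2: where the variance differs.** With 5% observed in both arms, the maximum-likelihood risks restricted to a difference of -7.5 points are about 3.2% and 10.7%. The null variance term is 0.032 x 0.968 + 0.107 x 0.893 = 0.126, against the 0.095 used in step 1.

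**Step 3: exact enumeration at 161 per arm.** For each interval, Binomial(161, azithromycin risk) x Binomial(161, placebo risk) probabilities are summed over all outcomes whose lower 97.5% limit exceeds -0.075. Power is taken with equal risks. Error is taken with the placebo risk 7.5 points higher.

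| Interval | Power, 5% vs 5% | Error, 5% vs 12.5% | Error, 2% vs 9.5% |
|---|---|---|---|
| Wald | 80.0% | 1.60% | 2.14% |
| Agresti-Caffo | 78.4% | 1.52% | 1.88% |
| Hauck-Anderson | 76.6% | 1.27% | 1.59% |
| Continuity-corrected Wald | 73.1% | 1.01% | 1.37% |
| Newcombe | 71.8% | 1.18% | 0.94% |
| Score (Miettinen-Nurminen, Farrington-Manning) | 71.4% | 1.08% | 0.94% |

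Over azithromycin risks up to 30%, the maximum error is 1.27% for Miettinen-Nurminen and 1.30% for Newcombe. An exact unconditional test built on the score statistic stays below 1.25% and has 71.4% power. No row gives 80% power with 1.25% error.

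**Step 4: dependence on the true risk** (same risk in both arms, power):

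| Risk | Wald | Score | Newcombe |
|---|---|---|---|
| 2% | 98.4% | 94.1% | 94.1% |
| 3% | 93.9% | 86.6% | 86.6% |
| 4% | 87.3% | 78.8% | 78.9% |
| 5% | 80.0% | 71.4% | 71.8% |
| 6% | 72.6% | 64.7% | 65.7% |

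**Step 5: can the choice change a conclusion?** Take 8/161 events on azithromycin and 10/161 on placebo. The difference is -1.24 points with a Wald standard error of 2.56 points, so the Wald lower limit is -1.24 - 2.241 x 2.56 = -6.98 points and non-inferiority is declared. The Newcombe limit is -7.56 and the Miettinen-Nurminen limit -7.63, so it is not. For 3/161 against 7/161 the three limits are -6.81, -7.84 and -7.93, with the same split.

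**Step 6: the at-least-one guarantee.** The time-to-normalization test needs 4 x 9.505 / ln(0.7)² = 298.9 events, and 298.9 / 0.99 gives 302 patients as printed. With 322 patients and 99% events there are about 318 events, and power is Φ(0.357 x √(318/4) - 2.241) = 82.6%. That endpoint alone meets the guarantee.

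**The case against.** The strongest reply is that nothing has been miscalculated. The 322 follows exactly from the stated inputs and a cited textbook method, and a nominal level met only approximately by a large-sample formula is ordinary planning practice. The detailed methods, including the type of interval, belong to the separate statistical analysis plan. The trial's success criterion needs only one of the two tests.

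Much of this stands, and it rules out several stronger readings that a reader might infer:

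- **That 322 is an arithmetic error.** It is not; step 1 reproduces it.
- **That the trial will run its safety test at an inflated error.** The protocol does not choose Wald. The 1.60-2.1% error and the changed conclusions in step 5 apply only if Wald is used.
- **That the trial is underpowered.** The at-least-one guarantee holds on the efficacy endpoint alone.
- **That the shortfall is always 8-9 points.** That applies at 5%, which section 5.1 gives as the upper end of its expectation. At 4% it is about 1 point, and at 3% there is none.
- **That the literature cited in section 5.1 fixes the risk at the low values where Wald is worst.** One cited study reports re-admission "in 2% receiving beta-lactam plus macrolide combination therapy", and the other 0.6% with combination therapy. Those are re-admissions with an unknown share of *Mp* infection. The trial endpoint also counts first admission and ICU transfer.

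What does not stand is that the analysis plan can settle the matter by naming an interval. The size and its claimed properties are fixed in the protocol. Naming an error-controlling interval makes the 80% untrue at the design assumptions, and naming Wald makes the 1.25% untrue.

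**Conclusion.** The point holds as a mismatch between two stated properties of one co-primary test. At 161 per arm, 5% risk in both arms and a -7.5-point margin, the design offers either about 80% power with 1.60% error (Wald), or about 71-72% power with error at about 1.25% or below (score or Newcombe). The other intervals checked fall between these without delivering both figures. If Wald were used, the bound on the overall one-sided error would be 1.25% + 1.60% = 2.85% at the design point instead of 2.5%.

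The blinded review does not remove the gap. It updates the risk but keeps the formula, so a pooled risk of 5% would return 322 again with score-interval power still at 71.4%.

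These results assume equal arms of 161 and independent binomial outcomes. The power figures also depend on the true risk, as step 4 shows. The correction is worth making because it concerns the safety claim and costs little; it does not put the declared success criterion at risk.

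**What to change.** 1. Decide the ARD test with a Miettinen-Nurminen/Farrington-Manning score interval (or Newcombe), and exclude the plain Wald interval. Section 11.4.2 is the natural place; the statistical analysis plan would also serve.
2. In section 11.2 and the synopsis, state the power of this endpoint at 322 evaluable patients as about 71-72% at 5% risk (about 79% at 4% and 87% at 3%). Keep the 80% at-least-one statement, and say that it rests on the time-to-normalization endpoint.
3. In section 11.4.4, report the chosen interval's power at the pooled risk alongside the recalculated size, so that the unpooled formula's result is not presented as 80%.

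The cost is a few sentences and one standard software option. The downside is a less favourable stated power for the safety co-primary. Enrolment of 376 can stay. Only if the sponsor wants 80% for this endpoint at 5% risk would the size have to rise, to about 374 (Newcombe) or 384 (Miettinen-Nurminen) evaluable patients. That is 374 / 0.855 = 438 or 384 / 0.855 = 450 enrolled, rounded up.
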